## 2.3 Rationale

To confirm the safety and efficacy of linac based VMAT for myeloablative TBI treatment delivery in patients with hematologic malignancies. VMAT-based TBI can reduce the lung dose, improve target coverage, and reduce dose heterogeneity with the goal of improving the therapeutic ratio of TBI. VMAT-based TBI can take advantage of image guidance using OBI and EPID, as well as in-vivo dosimetry using EPID. In addition, since the patient is treated on the linac couch, certain RNV safety features become available.

## 2.4 Potential Risks & Benefits

### 2.4.1 Known Potential Risks

There are known risks of any ASCT with myeloablative regimens including TBI including death. There are also many known late risks of TBI such as cataracts, cardiac toxicity, pulmonary toxicity, sterility, endocrine

#### CONFIDENTIAL

This material is the property of the NYU School of Medicine and Langone Medical Center. Do not disclose or use except as authorized in writing by the study sponsor

abnormalities, and secondary malignancy. These risks, especially secondary malignancy, are potentially higher for adolescents and young adults. This study introduces the added element of linac based VMAT TBI.

One potential risk of linac based VMAT TBI is that a higher dose rate will be used for treatment delivery as compared with conventional methods of delivering TBI and this could potentially result in higher rates of idiopathic pneumonia syndrome.

Another potential risk of linac based VMAT TBI is that the lower dose to the lungs and kidneys could result in an increased risk of relapse. It should be noted, however, that most conventional methods for TBI block dose to the lung using lung blocks or other methods so in that sense, the use of VMAT to limit dose the lung is not unique. Furthermore, there is some preliminary data on total marrow irradiation (TMI) in which organs such as the lungs and kidneys are intentionally spared completely and the preliminary outcomes show the validity of this approach.

There could be other risks associated with a novel-treatment approach including the risks for possible errors in treatment delivery. As detailed below, many measures are taken to ensure accurate and precise dose delivery to minimize the risk of any errors.

There could be other unknown or unanticipated risks with regard to toxicity and efficacy of linac based VMAT TBI that are not present with conventional methods of TBI delivery.

#### **2.4.2 Other Risks of Study Participation**

Additional risks to study participation include breach of confidentiality. Privacy protection procedures are in place and good clinical practice guidelines will be followed throughout the study to minimize the risks associated with breach of confidentiality.

#### **2.4.3 Known Potential Benefits**

A potential benefit of linac based VMAT TBI, as opposed to our current approach of using opposed laterals to deliver TBI, is that we can minimize the dose to the lungs, without compromising coverage in the thoracic region outside of the lungs. This will have the potential of reducing the risk of idiopathic pneumonia syndrome while maximizing the effectiveness of TBI. We limit the mean dose to the kidneys, which has the potential to prevent renal dysfunction.

Since the initial writing of this protocol, Stanford has published their VMAT TBI experience which includes primarily pediatric patients (23/35 patients <18 years old). Their series includes 35 patients treated with VMAT TBI, 13 with doses of 12Gy or higher as per this protocol. Their dose objectives are similar to ours with a D90% $\geq$ 100% for the PTV body a Dmax $\leq$ 120%, Dmean of lungs  $\leq$ 660cGy. Of note, they also constrict their kidney dose and lens dose for myeloablative regimens. Their toxicity data (unpublished, data courtesy of [name] and [name]) is very favorable with a 4% rate of grade 2 pneumonitis (n=1, present before RT), 4% rate of grade 1 nephrotoxicity (n=1, present before RT), 40% diarrhea (4% grade 3), 56% rate of fatigue (all  $\leq$  grade 2), 76% rate of nausea (4% grade 3), 84% rate of mucositis (36% grade 3), and 16% rate skin toxicity (all  $\leq$  grade 1).

Also since the initial writing of this protocol, a review of dose rate and pulmonary toxicity was published which bears mention given its relevance to this protocol. Vogel et al summarize the literature on the effect of dose rate and pulmonary toxicity after conventional TBI. Of a total of 53 studies which report risk factors for pulmonary toxicity after TBI, 13% report dose rate as an added risk. In one of the studies included (Barrett et al., 1982), dose rate is associated with incidence of pulmonary toxicity only for lung dose  $\geq$ 9Gy. This review concludes that for TBI delivered with traditional planning techniques, a dose rate  $\leq$ 15cGy/minute is ideal and that total lung dose is another relevant parameter. The clinical data using IMRT or VMAT techniques, in which dose rates tend to be much higher is more limited. A report of radiation-related toxicities using organ sparing total marrow irradiation delivered intensity modulated radiation therapy with tomotherapy (n=142 patients), the dose rate was 200cGy/minute and the crude rate of radiation pneumonitis was 0.7% at a median follow up of

CONFIDENTIAL

This material is the property of the NYU School of Medicine and Langone Medical Center. Do not disclose or use except as authorized in writing by the study sponsor

2 years. The Stanford group changes the dose rate from the 600MU/minute default to 100-200 MU/minute for the beams treating the lungs to keep the average lung dose rate <20cGy/minute. Thus, the limited data there is on TBI delivered with IMRT technique does not show a link between increased dose rate and pneumonitis.

### **3 Objectives and Purpose**

#### **3.1 Primary Objective**

To estimate the proportion of subjects who achieve excellent target coverage while sparing the lungs. Specifically, excellent target coverage requires that the following 3 dosimetric parameters levels have been achieved:

- 1)  $V100\% \geq 90\%$  (90% of PTV volume getting 100% of the dose).
- 2)  $D98 > 85\%$  (98% of the volume getting at least 85% of the dose).
- 3) Mean Lung dose <900cGy.

#### **3.2 Secondary Objectives**

- 1) To estimate the cumulative incidence rate of idiopathic pneumonia syndrome in the first 100 days after transplant.
- 2) To estimate the cumulative failure rate (including acute GVHD, transplant related mortality or death) during the first 100 days post transplant following full-dose TBI delivered with linac based VMAT
- 3) To estimate the event Free Survival (EFS)
- 4) To estimate the following:
  - a. Proportion of subjects who have achieved a mean dose to each kidney (Dmean) < 11Gy.
  - b. Proportion of subjects who have achieved a maximum dose to 2cc of the entire body (D2cc) <130% of Rx dose.
  - c. Proportion of subjects who have achieved a maximum dose to 0.03cc of OARs < 120% of Rx dose.
- 5) To summarize the subject-specific quality assurance (PSQA) for each treatment plan.

#### **3.3 Exploratory objectives**

- To explore the dosimetric consequences on the PTV, lungs and kidneys as a result of subject setup variations
- To analyze the in vivo transit dosimetry using SNC PerFraction (Fraction N) for dose tracking and correlation with subject setup
- To compare the linac based VMAT TBI vs. conventional TBI for treatment planning time
- To compare the linac based VMAT TBI vs. conventional TBI for treatment delivery time
- To conduct a cost analysis of linac based VMAT TBI vs. conventional TBI
- To explore the dosimetric consequences on the PTV, lungs, and kidneys as a result of subject setup variations.
- To analyze the in vivo transit dosimetry using SNC PerFraction (Fraction N) for dose tracking and correlation with subject setup
- To compare the linac based VMAT TBI vs. department's previous cases for treatment planning time
- To compare the linac based VMAT TBI vs. department's previous cases for treatment delivery time
- To conduct a cost analysis of linac based VMAT TBI vs department's previous cases

CONFIDENTIAL

This material is the property of the NYU School of Medicine and Langone Medical Center. Do not disclose or use except as authorized in writing by the study sponsor

## 4 Study Design and Endpoints

### 4.1 Description of Study Design

Non-randomized phase II single-institution trial in which patients who consent to the trial will be treated with linac based VMAT TBI as part of their conditioning regimen for transplantation. The investigators include doctors with expertise in both adult and pediatric bone marrow transplant as well as both adult and pediatric radiation oncologists. NYU Langone Health has both an adult and a pediatric bone marrow transplant program.

### 4.2 Study Endpoints

#### 4.2.1 Primary Study Endpoints

To achieve excellent coverage while sparing the lung as quantified by meeting the following dosimetric parameters: (all parameters must be met).

1.  $V100\% \geq 90\%$  (90% of PTV volume getting 100% of the dose).
2.  $D98 > 85\%$  (98% of the volume getting at least 85% of the dose).
3. Mean Lung dose  $< 900\text{cGy}$ .

#### 4.2.2 Secondary Study Endpoints

1. The occurrence of non-infectious pneumonia syndrome in the first 100 days after transplant.  
Non-infectious pneumonia syndrome is defined by the American Thoracic Society as at least 1 of the following (i, ii, iii) without concurrent infection detected on blood culture, bronchoalveolar lavage, lung biopsy or sputum. Multilobar infiltrates on chest radiograph or computed tomography (CT)
  - ii. Symptoms and signs of pneumonia including dyspnea, cough, cyanosis, hypoxia or pyrexia
  - iii. New or increased restrictive patterns on pulmonary function testing or increased alveolar to arterial oxygen difference.
  - There must be no concurrent cardiac dysfunction, acute renal failure, or iatrogenic fluid overload as etiology for pulmonary dysfunction.
2. Occurrence of acute GVHD, transplant related mortality, or mortality in the first 100 days following transplant
3. Event Free Survival (EFS): interval from day 0 to date of first objective disease progression or relapse or death from any cause. Subjects without these failures will be censored at the last date that they were assessed and deemed failure free. The date of disease progression or relapse will be determined by the transplant team (medical oncology investigators) as per each disease-specific definition of progression or relapse. Day 0 is the day of the transplant.
4. Additional Dosimetric parameters of the linac based VMAT TBI plan not included in the primary endpoint:
  - Mean dose to each kidney ( $D_{\text{mean}}$ )  $< 11\text{Gy}$ .
  - Maximum dose to 2cc of the entire body ( $D_{2\text{cc}}$ )  $< 130\%$  of Rx dose.
  - Maximum dose to 0.03cc of OARs  $< 120\%$  of Rx dose.
5. Subject-specific quality assurance (PSQA) for each treatment plan:

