Myeloablative regimens are associated with treatment-related or non-relapse-related mortality rates of approximately 20-30%. The most common toxicity of TBI based conditioning regimens is radiation-induced interstitial pneumonitis. When delivered as a single high-dose (8-10 Gy) fraction, TBI is associated with a 50% risk of radiation-induced interstitial pneumonitis with a 50% fatality rate. Even with fractionation, pneumonitis can occur in up to 25% of patients though the risk of fatal events is reduced. The reported incidence of non-infectious pneumonitis or idiopathic pneumonia syndrome (IPS) after TBI-based myeloablative conditioning regimens range from 7% to 35%. In a recently published single institution series with 202 patients in which 13.2 Gy TBI was delivered with opposed lateral beams, IPS occurred in 21% of patients at a median of 16 days with a mortality rate of 45%. Those undergoing TBI with a high-dose rate (HDR) had a nearly 3-fold increase in IPS (29%) compared with those receiving low-dose rate (LDR) TBI

CONFIDENTIAL

This material is the property of the NYU School of Medicine and Langone Medical Center. Do not disclose or use except as authorized in writing by the study sponsor

(10%). Lung shielding was not used. Other factors, aside from dose rate, associated with IPS on multi-variate analysis were use of lower energy, a higher comorbidity index, and the specific conditioning regimen used. Another single institution series reviewed 77 patients receiving once-daily TBI between years 2000 and 2016. In this study, the cumulative rate of pulmonary toxicity was assessed. Dose rate, total dose and conditioning regimen were significant factors for the development of pulmonary toxicity. It is important to note that the definition of HDR versus LDR is not standardized for different studies and while Gao et al., defined the HDR vs. LDR dose rate cut-off at 15 cGy/min, Kim et al., defined the dose rate cut-off at 6 cGy/min.

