### **7.2.2 Other Assays or Procedures**

Imaging will be performed as SOC following ASCT as clinically indicated. PFTs will be performed one year out.

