## 10 Statistical Considerations

The study is designed to estimate the proportion of patients who achieve excellent coverage while sparing the lung as quantified by meeting the following dosimetric parameters: (all parameters must be met).

1. V100%= >90% (90% of PTV volume getting 100% of the dose).
2. D98>85% (98% of the volume getting at least 85% of the dose).
3. Mean Lung dose <900cGy.

The key secondary objective is to estimate the cumulative incidence of non-infectious idiopathic pneumonia syndrome (IPS) within the first 100 days post transplant.

Non-infectious pneumonia syndrome is defined by the American Thoracic Society as at least 1 of the following (i, ii, iii) without concurrent infection detected on blood culture, bronchoalveolar lavage, lung biopsy or sputum.

- i. Multilobar infiltrates on chest radiograph or computed tomography (CT)
  - ii. Symptoms and signs of pneumonia including dyspnea, cough, cyanosis, hypoxia or pyrexia
  - iii. New or increased restrictive patterns on pulmonary function testing or increased alveolar to arterial oxygen difference
- There must be no concurrent cardiac dysfunction, acute renal failure, or iatrogenic fluid overload as etiology for pulmonary dysfunction.

Additional secondary objectives include:

Time to the first occurrence of acute GVHD, transplant related mortality or death in the first 100 days will be estimated.

Event Free Survival (EFS): interval from date of transplant to date of first objective disease progression or relapse or death from any cause. Patients without these failures will be censored at the last date that they were assessed and evaluated as failure free.

Additional Dosimetric parameters of the linac based VMAT TBI plan not included in the primary endpoint:

- Mean dose to each kidney (Dmean) < 11Gy.
- Maximum dose to 2cc of the entire body (D2cc) <130% of Rx dose.
- Maximum dose to 0.03cc of OARs < 120% of Rx dose.

Patient-specific quality assurance (PSQA) for each treatment plan:

- A pass rate of higher than 90% of points using a gamma criterion 5% at 3 mm and a dose threshold of 10% is required between the delivered dose to an array of detectors and the planned dose for each individual VMAT field.

Exploratory endpoints are:

- Dosimetric consequences on the PTV, lungs and kidneys as a result of patient setup variations
- in vivo transit dosimetry using SNC PerFraction (Fraction N) for dose tracking and correlation with patient setup

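### The IPS rule in Sections 4.2.2 and 10 lets one non-specific sign count as the key secondary safety event, with no infiltrate, abnormal physiology or work-up required

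*Combined protocol and SAP*

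**What the plan says.** Section 4.2.2, item 1, defines the event as follows: "Non-infectious pneumonia syndrome is defined by the American Thoracic Society as at least 1 of the following (i, ii, iii) without concurrent infection". Section 10 repeats the rule and names where an infection would have to be found: "defined by the American Thoracic Society as at least 1 of the following (i, ii, iii) without concurrent infection detected on blood culture", lavage, biopsy or sputum. The three criteria are:

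- (i) multilobar infiltrates on chest film or CT;
- (ii) "Symptoms and signs of pneumonia including dyspnea, cough, cyanosis, hypoxia or pyrexia";
- (iii) abnormal physiology, meaning either a restrictive lung function pattern that is new or worse, or a widened alveolar-arterial oxygen difference.

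A further condition reads: "There must be no concurrent cardiac dysfunction, acute renal failure, or iatrogenic fluid overload as etiology for pulmonary dysfunction".

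Section 10 calls the cumulative incidence of IPS to day 100 the key secondary objective. Section 7.2.1 requires no particular laboratory test or imaging. It says that standard-of-care results will be weighed in deciding the cause of pulmonary symptoms and whether the endpoint is met. Visit 6 (Section 7.3.2.2), between 100 and 150 days, reviews the interval history and any thoracic imaging done. Lung function tests are scheduled before transplant and at one year: "PFTs will be performed one year out" (Section 7.2.2).

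Section 2.1 cites an incidence of 7% to 35% for non-infectious pneumonitis or IPS across several series. It also cites one series with 21% overall, 29% at high dose rate and 10% at low dose rate. Section 10.1 describes the secondary analyses as mainly descriptive.

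**The concern.** The three criteria are alternatives, and the signs inside criterion (ii) are alternatives too. Criterion (ii) can therefore carry a case alone, on one sign that has many causes after myeloablative conditioning. The infection exclusion works only if an infection was looked for and found, and the protocol does not require anyone to look.

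Section 2.4.1 names IPS as the risk that the higher dose rate might raise, and Section 2.4.3 names it as the harm that lung sparing might reduce. A loose rule in an open single-arm study has two possible effects. It may add cases that are not lung injury, or investigators may narrow it case by case without a written rule. In either event a reader could not tell what the reported rate measures.

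**Working it through.** **1. Does the rule allow a single-sign case?** Take a subject with cough that the treating team attributes to pneumonia, with no chest imaging, no microbiology, and no cardiac, renal or fluid cause.

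| Element | Source | Result |
|---|---|---|
| At least one of (i), (ii), (iii) | 4.2.2 and 10 | Met by (ii) alone |
| No infection detected | 4.2.2 and 10 | Met, because nothing was tested |
| No cardiac, renal or fluid cause | 4.2.2 and 10 | Met |
| Minimum work-up | 7.2.1 | None required |
| Review of cause | 7.2.1, 7.3.2.2 | Takes place, but with no decision rule |

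The subject can be counted. The same rule stands in both sections, so a slip in one place is unlikely.

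**2. The plan's own figure.** There is none for IPS. The only design calculation, in Section 10.1, is a lower limit of 68.9% for the dosimetric endpoint. It reproduces: the one-sided 95% Clopper-Pearson lower limit at 29/35 is 68.9%. It has no bearing on this point.

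**3. How far could the rate move?** Let p be the true IPS rate and f the share of subjects without IPS who are counted through one non-specific sign. Assume that all true cases are found, and treat the rate as a simple proportion. Then

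observed rate = p + (1 - p) × f.

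The value of f is an assumption; no figure in the documents fixes it. At p = 10%, the low dose rate figure in Section 2.1:

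| f (assumed) | Observed rate | Expected count in 35 |
|---|---|---|
| 0% | 10% | 3.5 |
| 5% | 0.10 + 0.90 × 0.05 = 14.5% | 5.1 |
| 10% | 0.10 + 0.90 × 0.10 = 19% | 6.7 |
| 20% | 0.10 + 0.90 × 0.20 = 28% | 9.8 |
| 30% | 0.10 + 0.90 × 0.30 = 37% | 12.9 |

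The f that turns 10% into the 29% cited for high dose rate is (0.29 - 0.10)/0.90 = 21%. The f that reaches 35%, the top of the cited range, is (0.35 - 0.07)/0.93 = 30% from a true rate of 7%, and (0.35 - 0.21)/0.79 = 18% from a true rate of 21%.

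**4. Would the confidence interval show it?** No. With 35 subjects the exact two-sided 95% interval is 1.8% to 23.1% for 3 cases and 8.4% to 36.9% for 7 cases. These intervals reflect sampling error only. Misclassification moves the estimate and the interval together.

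**The case against.** The text has brakes. Criterion (ii) speaks of signs of pneumonia, the exclusion clause presupposes pulmonary dysfunction, and Sections 7.2.1 and 7.3.2.2 provide for a review of cause and of thoracic imaging. A reader might infer that any culture-negative fever with a clear chest is automatically an IPS event. The documents do not support that: someone must first attribute the fever to pneumonia. The brakes soften the rule, but none is a stated requirement and no adjudication step is described, so the gap stays open.

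A reader might also infer that the cited series used a stricter definition, perhaps because the 21% series had 45% mortality among its cases. Section 2.1 gives no case definitions or time windows, so neither comparability nor its absence can be shown. No test, stopping rule or sample size uses the IPS rate.

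Nor is criterion (iii) empty before day 100. The scheduled lung function tests miss the window, but an oxygen-difference measurement or an unscheduled test could meet it.

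The last objection is about the remedy. Chest imaging is done only when clinically indicated, so a rule that demands infiltrates may undercount a safety event. That stands, and it is why both counts are needed. Grading from 1 to 5 in Section 8.4.1 helps to describe severity, but the endpoint has no grade threshold.

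**Conclusion.** The concern holds in a limited form. The rule as written lets one non-specific sign attributed to pneumonia count as the key secondary safety event, without infiltrate, abnormal physiology or any required search for infection. Its effect on the rate is unknown. Under the assumed model, with full detection of true cases, a misclassified share of 10% to 21% of non-cases turns a true 10% into 19% to 29%. The upper end equals the whole difference between the low and high dose rate figures in Section 2.1.

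The damage is to the reading of the result, including any informal comparison with 7% to 35%. The dosimetric primary endpoint is untouched. Whether the society statement in reference 6 really joins the criteria as alternatives cannot be settled from these documents. This should be fixed before cases are classified; a later change would look data-driven.

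**What to change.** 1. Check the joining rule against reference 6. If it differs, correct it in Sections 4.2.2 and 10.
2. Classify every treated subject at day 100 or death, whichever comes first, from the standard-of-care record. Record which of (i), (ii) and (iii) were met. Visit 6 already reviews this material for survivors; for subjects who die earlier, the same record review is done without a visit.
3. Report as the main estimate a specific count: infiltrates plus (ii) or (iii), with the exclusions applied, unless reference 6 gives a different rule. Report the any-one count beside it as a sensitivity result.

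The cost is a wording change in two sections and a few fields on the case report form. No extra imaging or tests are needed. The drawback is that an event in a subject without chest imaging appears only in the sensitivity count, so the two counts must always be shown together.

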#### CONFIDENTIAL

This material is the property of the NYU School of Medicine and Langone Medical Center. Do not disclose or use except as authorized in writing by the study sponsor

- A pass rate of higher than 90% of points using a gamma criterion 5% at 3 mm and a dose threshold of 10% is required between the delivered dose to an array of detectors and the planned dose for each individual VMAT field.

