### **CONFIDENTIAL**

This material is the property of the NYU School of Medicine and Langone Medical Center. Do not disclose or use except as authorized in writing by the study sponsor

- Patient-specific QA will be performed prior to first treatment.
- Prior to initiating treatment, images will be acquired with the on-board imaging system including kV, MV and CBCT. Images will be reviewed by an attending radiation oncologist before the first treatment is delivered.
- Positioning shifts will be applied as deemed necessary to achieve correct patient positioning.
- Treatment will be delivered. During treatment, transit dosimetry will be obtained using the EPID.

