## 6.2 Study Agent Accountability Procedures

Quality assurance for the linear accelerator, OBI, EPID and MLC system will be routinely assessed as part of the current department policy and procedures (P&P) in accordance with the American Association of Physicist in Medicine (AAPM) task group 142.

All upper body plans will include volumetric modulated fields and will undergo patient specific QA (PSQA) prior to treatment using the electronic portal imaging device (EPID). The recorded data will be analyzed using two systems: SNC PerFraction (Fraction 0 module) and Varian Portal Dosimetry. Each field will be required to pass, with a passing rate of at least  $\geq 90\%$  using a gamma criterion of 5% at 3mm using both tools, with a preferred passing rate of  $\geq 95\%$  using a gamma criterion of 3% at 3mm.

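### Secondary endpoint 5 (PSQA) reuses almost the same threshold that each field must meet before treatment, so a pass/fail result says little unless initial measurements are summarised

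*Combined protocol and SAP*

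**What the plan says.** **The endpoint.** Section 4.2.2, item 5, sets this as a requirement: "A pass rate of higher than 90% of points using a gamma criterion 5% at 3 mm", with a 10% dose threshold. The comparison is "between the delivered dose to an array of detectors and the planned dose for each individual VMAT field". Section 10 repeats this definition.

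**The treatment requirement.** Section 6.2 states: "All upper body plans will include volumetric modulated fields and will undergo patient specific QA (PSQA) prior to treatment". The measurement there uses the electronic portal imaging device (EPID) and is analysed in two software systems. It continues: "Each field will be required to pass, with a passing rate of at least" 90%, "using a gamma criterion of 5% at 3mm using both tools, with a preferred passing rate of" at least 95% at 3%/3 mm. The workflow list in Section 2.2 confirms the timing: "Patient-specific QA will be performed prior to first treatment".

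**The objective and the analysis.** Section 3.2, objective 5, reads: "To summarize the subject-specific quality assurance (PSQA) for each treatment plan". Section 10.1 says that secondary endpoints are analysed mainly descriptively. It gives no PSQA-specific measure, and its analysis set is treated subjects who go on to transplant.

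**Exceptions to study delivery.** Sections 6.1.2 and 6.2 allow treatment on another machine, or with a conventional backup plan, if the study linac is unavailable.

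**The concern.** The only criterion that endpoint 5 states is, in substance, the level a field has to reach before the subject may be treated. Counting passes among treated subjects then counts plans already screened on nearly the same test. A reported rate near 100% would look like evidence that VMAT TBI plans can be delivered reliably, when it would mainly show that the pre-treatment check was applied.

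Two quantities would be more informative: how fields performed at their initial measurement, and how far they sit above the threshold. The stricter 3%/3 mm level in 6.2 would help with the second, but neither the endpoint nor the statistics section uses it. In addition, 4.2.2 and 10 do not describe the test in the same way as 6.2, so an analyst cannot be sure which measurement feeds the endpoint.

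**Working it through.** **Step 1. Compare the two definitions.**

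| Feature | Endpoint (4.2.2, 10) | Treatment requirement (6.2) |
|---|---|---|
| Gamma criterion | 5% at 3 mm | 5% at 3 mm |
| Pass level | above 90% of points | 90% or more |
| Low-dose threshold | 10% | not stated |
| Device | a detector array | EPID, two software systems, both must pass |
| Unit | each VMAT field | each field |
| Plans named | each treatment plan | upper-body plans |
| Stricter level | none | 95% or more at 3%/3 mm, preferred |

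The criterion and unit agree, and the pass levels differ only at exactly 90%. Device, software and scope are worded differently.

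**Step 2. What a pass/fail result would measure.** The quantity reported would be the pass rate given that the subject was treated. If 6.2 is enforced, treatment itself depends on passing. The reported rate is then near 100% whatever the initial pass rate was. The exceptions are a field at exactly 90%, a field outside the scope of 6.2, a difference between measurement systems, or a subject treated with a backup plan.

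**Step 3. Illustration of size.** The plan gives no PSQA figure to reproduce; its one computed design figure (a lower limit of at least 68.9%, Section 10.1) concerns the primary endpoint and has no bearing here. The documents give no initial pass rate either, so the rates below are assumed. For simplicity the illustration counts subjects, treated as independent, with n = 35 (Section 5.6); the endpoint's own unit is the field.

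- If all 35 pass, the exact two-sided 95% lower limit is 0.025^(1/35) = 90.0%, so the interval is 90.0% to 100%.
- If nothing were screened out, the chance that all 35 pass is p^35.

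| Assumed subject-level initial pass rate p | Count near 35p, with exact 95% interval | p^35 |
|---|---|---|
| 80% | 28/35 (63.1% to 91.6%) | 0.04% |
| 90% | 32/35 (76.9% to 98.2%) | 2.5% |
| 95% | 33/35 (80.8% to 99.3%) | 16.6% |

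In each row, an enforced pre-treatment requirement with no exceptions would turn the reported figure into 35/35. A screened 35/35 therefore cannot distinguish these situations.

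**Step 4. Does the plan ask for something more informative?** Objective 5 asks for a summary and 10.1 allows descriptive statistics, so a distribution of gamma pass rates is permitted. However, no section says whether the initial or final measurement is summarised, what happens to the data when a field fails, whether 3%/3 mm values are kept as study data, or how subjects without qualifying PSQA are counted.

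**The case against.** The strongest reply is that the plan never commits to a pass/fail proportion. Objective 4 asks three times for a proportion of subjects, while objective 5 asks only for a summary. A summary of actual pass rates would show how far fields sit above 90%. This stands: it would be wrong to say that such information will be lost. What remains is that the summary is unspecified and that the only criterion attached to the endpoint is the treatment threshold.

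A reader might infer that every treated subject passes by construction, so that the result is fixed at 35/35. The documents do not support that. Backup delivery may leave a subject with no study VMAT field, yet that subject stays in the analysis set if transplanted. A field at exactly 90% meets 6.2 but not 4.2.2. No rule for a failed field is written, so its correction before treatment is only an inference.

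A reader might also infer that initial 3%/3 mm results are already being collected. A preferred rate implies that the value is computed, but recording it as study data is not stated.

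The differences in wording may be smaller than they look. An EPID can be read as a detector array. Section 6.2 says that upper-body plans contain volumetric modulated fields and is silent on lower-body plans, so the two scopes may coincide. That is possible, but the reader should not have to guess.

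Finally, in vivo transit dosimetry is an exploratory endpoint (4.2.3), and 6.2 says its absence does not hold up treatment. It does give separate evidence on delivery. It is acquired during treatment, however, so it cannot show how often a plan failed its initial check.

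**Conclusion.** The point holds in a limited form. Endpoint 5 uses essentially the criterion that 6.2 requires before treatment. If 6.2 is enforced, a pass/fail reading among treated subjects is near 100% by design and says little about how reliably plans can be delivered. The more discriminating 3%/3 mm level is absent from the endpoint and from the statistics section, and the measurement occasion is not stated.

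The 35/35 figure, with its interval of 90.0% to 100%, only illustrates the problem: the plan specifies no PSQA proportion or exact interval, and the unit is the field. The conclusion assumes that the pre-treatment requirement is applied as written and that the endpoint is read as pass/fail.

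This is a cheap improvement to one descriptive secondary endpoint. The primary endpoint and the sample size are unaffected.

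**What to change.** In Sections 4.2.2, 10 and 10.1:

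- Define endpoint 5 as the initial-measurement gamma pass rate for each VMAT field, before any re-measurement or re-planning.
- Report the median and range at 5%/3 mm and at 3%/3 mm, and the proportion of fields at or above 95% at 3%/3 mm.
- Report the number of fields that failed, were re-measured or were re-optimised.
- Report separately subjects treated with a backup plan and without qualifying PSQA.
- Reconcile 4.2.2 and 10 with 6.2 on device and software, on above 90% versus 90% or more, and on which plans' VMAT fields are covered.

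Leave the treatment requirement unchanged; only the reporting changes.

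The cost is SAP wording, plus retaining first-attempt and 3%/3 mm results as study data. This should be specified prospectively, because first-attempt values may not be recoverable later. The reported figure may also fall below 100%.
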